## 2.8.4 Other safety data

### 2.8.4.1 ECG data

The ECG variables (Heart rate, QRS duration) will be summarized by reporting actual and change from baseline values using descriptive summary statistics and qualitative changes as shift from baseline will be described. Additionally, data will be listed, and any other information collected will be listed as appropriate.

### 2.8.4.2 Vital signs

Data from vital signs will be summarized by reporting descriptive summary statistics for both actual and change from baseline at each available visit with visit 101 as baseline; furthermore, various threshold flags will also be used to determine incidences of notable values, which will be presented in tables and notable values will be flagged in the listings.

Patients with notable vital signs as defined below will be summarized:

- Pulse rate:
  - Low:  $\leq 50$  bpm and decrease from baseline higher or equal to 15 bpm
  - High:  $\geq 120$  bpm and increase from baseline higher or equal to 15 bpm
- Systolic blood pressure (SBP):
  - Low:  $\leq 90$  mmHg and a decrease from baseline higher or equal to 20 mmHg
  - High:  $\geq 180$  mmHg and increase from baseline higher or equal to 20 mmHg
- Diastolic blood pressure:
  - Low:  $\leq 50$  mmHg and a decrease from baseline higher or equal to 15 mmHg
  - High:  $\geq 105$  mmHg and increase from baseline higher or equal to 15 mmHg.

### 2.8.4.3 Liver and renal events

Detailed information of liver and renal event is collected only if patients report any.

[figure not shown]
[figure not shown]
The following eCRF pages will be collected for the reported liver event.

- Acetaminophen/Paracetamol
- Liver event overview: details of clinical signs and symptoms, event related to study drug, other alternative diagnoses etc.
- Local laboratory liver function test
- Autoimmune
- Viral serology
- Medical history possibly contributing to liver dysfunction.
- Pathology
- Drugs of abuse history
- History of alcohol use
- Imaging

The following eCRF pages will be collected for renal events include:

- Diagnosis page
- Follow up pages: details of clinical signs and symptoms
- Overview: other alternative diagnoses
- Renal function tests
- Local lab results
- Pathology
- Imaging

## 2.11 Interim analysis

Two interim analyses of tolerability and safety will be carried out during the study when 30% and 60% of the patients have completed the visit at 10-weeks after Randomization (Visit 199).

Details will be pre-specified in the Charter of the DMC.

The review will include the following analyses:

- AEs leading to permanent discontinuation of LCZ696
- AEs reported leading to down-titration of LCZ696 or temporary discontinuation
- Incidence of AEs of interest
- Concomitant medication changes when down-titration was implemented
- Compliance with the washout from ACEi or discontinuation of ARBs

The DMC will also monitor all adverse outcomes during the trial and weigh them against the potential benefits of treatment. The DMC will in particular monitor:

- Angioedema
- Hyperkalemia
- Liver and Renal Dysfunction
- Hypotension
- Pregnancy

When considering whether to stop any active treatment arm of LCZ696 for safety concerns the following points should be considered

- whether observed adverse trends are compelling in terms of the amount of evidence
- whether observed adverse trends outweigh the potential benefits of treatment.

If the study is terminated, all ongoing patients will be brought in for the end of study visits. Those incomplete patients which do not get to Week 10 (Visit 199) as a result of DMC study termination by the DMC, will be excluded from both the primary analysis and the supplementary primary analysis.

To ensure the DMC is provided all required information and to ensure the proper execution of the interim analysis an interim analysis plan will be prepared. This analysis plan will include a description of all statistical analyses to be conducted, specifications for the analysis data sets and the layout of tables, figures and listings. Analyses will be planned and conducted as specified in the Clinical Trial Protocol, unless specific monitoring requirements of the DMC necessitate a different approach. The Novartis trial team will be given the opportunity to provide comments and recommendations and the Novartis list of mandatory tables for a DMC safety report will be included.

The interim analysis will not bias the course of the trial. Firstly, the independent statisticians and programmer, as well as all DMC members, are not involved in the conduct of or decisions about the study. Secondly, the DMC deliberations remain confidential to members of the clinical trial team, as well as investigators and their staff. And finally, only the recommendation to terminate the trial, if at all, will be reported to the clinical trial team.

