Specific circumstances surrounding missed or rescheduled visits must be discussed with the study monitor. Missed or rescheduled visits SHOULD NOT LEAD automatically to patient discontinuation.

For patients who permanently discontinue LCZ696 during the Treatment Epoch (up to visit 199), irrespective of the treatment assignment group, the last date of LCZ696 administration will be entered in the drug administration records (DAR) page of the CRFs. However, the patient will be followed-up and should return to the site for all remaining visits up to Visit 199 (10 weeks after Randomization) but will not return for the Follow-up epoch.

Enrolled patients withdrawing from the study for any reasons during the Follow-up Epoch should be scheduled for a visit as soon as possible, at which time all of the assessments listed

for End of Study visit (EoS, Visit 299) will be performed. At this final visit all dispensed medication supplies should be reconciled and the Adverse Events and Concomitant Medications updated on their respective CRFs.

Page 40

Documentation of attempts to contact the patient who do not report for the EoS visit, and are lost to follow-up, should be recorded in the source documentation.

Table 6-1 Assessment table

Epoch	Screen- ing				Treatm	ent						F	Follow-เ	ір
Visit	1	101 Random -ization	Start date of Pre -discharge treatment	102 Discharge	Start date of Post- discharge	103	104	105	106	199 & TD and/or PPW	201	202	203	End of Study Visit 299 & TD and/or PPW
Day	-3-to-1	1				14§	28§							
Weeks AFTER Randomization						2§	4 §	6§	8§	10§	14 ^Φ	18 ^Ф	22 ^ф	26 ^ф
Weeks of follow-up											4	8	12	16
Obtain informed consent	Х													
Entry criteria review	Х													
Demography	X													
Medical History	Х													
Alcohol and smoking history	Х													
ECG	S	Х		Х						Х				Х
Signs & Symptoms	S	Х		X						Х				X
NYHA class		X		Х						Х				Х
Prior & Concomitant HF Medications	X Å	X		X _Φ		X	XΔ	XΔ	XΔ	XΔ	XΔ	XΔ	XΔ	X _Φ
Physical Exam	S													S
Height	Х													

Epoch	Screen- ing				Treatm	nent						F	Follow-เ	ір
Visit	1	101 Random -ization	Start date of Pre -discharge treatment	102 Discharge	Start date of Post- discharge	103	104	105	106	199 & TD and/or PPW	201	202	203	End of Study Visit 299 & TD and/or PPW
Day	-3-to-1	1				14§	28§							
Weeks AFTER Randomization						2§	4 §	6§	8 §	10§	14 ^Φ	18 ^Ф	22 [¢]	26 ^ф
Weeks of follow-up											4	8	12	16
Weight	S	Х		S						S				S
Vital signs	Х	Χ□		Х		Χ	Х	Χ	Χ	Х	Χ	Х	Х	X

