### **2.5.3 Handling of missing values/censoring/discontinuations**

In the primary analysis, no imputation will be used for any patients, who discontinue study therapy due to adverse events or abnormal laboratory values. All patients who prematurely discontinue, and do not achieve and maintain the target dose of LCZ696 200 mg bid at 10 weeks after randomization will be regarded as 10 week up-titration failures. Information of patients discontinuing study drug or participation in trial visits will be collected whenever possible and will be used in the analysis. In patients who could not be followed up for the primary endpoint, it is aimed to at least determine the vital status of the patients at the final visit.

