### **2.5.4 Supportive analyses**

In addition to the primary analysis, a supportive analysis will be carried out, based on evaluable patients in the SAF population where patients with administrative discontinuations (non-AE or non-death reasons) will be considered as non-evaluable, and thus excluded.

As a further supportive analysis, the primary analysis, will be repeated using the FAS population instead of the SAF population,

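### If the DMC stops the trial, whether a recently randomised patient enters the week-10 analysis depends on whether that patient has already failed

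*SAP*

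**What the plan says.** SAP 2.11 covers termination by the DMC. The patients concerned are "Those incomplete patients which do not get to Week 10 (Visit 199) as a result of DMC study termination", and they "will be excluded from both the primary analysis and the supplementary primary analysis". The criterion is the cause of the missed visit. The date of randomisation plays no part.

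SAP 2.5.3 gives the general rule. It takes "All patients who prematurely discontinue, and do not achieve and maintain the target dose" by week 10, and says that such patients "will be regarded as 10 week up-titration failures". It does not require that the patient could have reached week 10 before a stop. Protocol 9.4.3 carries the same failure rule without any termination exclusion, and SAP section 4 does not list the exclusion as a change from the protocol.

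Under SAP 2.5.4, in the supportive analysis, "patients with administrative discontinuations (non-AE or non-death reasons) will be considered as non-evaluable, and thus excluded". Discontinuations for adverse events and deaths therefore remain failures there. The further repeat in the FAS reuses the primary analysis, and so its rules.

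Protocol 5.5.9 says that stopping LCZ696 for good during the Treatment Epoch is not withdrawal from the study. Protocol section 6 adds that "the patient will be followed-up and should return to the site for all remaining visits up to Visit 199".

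**The concern.** Take two patients randomised on the same day, four weeks before a stop. One has died. The stop did not cause the missed Visit 199, so 2.11 does not reach this patient and 2.5.3 makes the patient a failure. The other is titrating well, and 2.11 removes that patient. No recent patient short of Visit 199 can enter as a success, so membership of the analysis depends on the outcome being analysed.

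At stake are the headline estimates of a stopped trial: the week-10 success rate in each arm and the risk ratio. SAP 2.11 states that the interim analysis will not bias the trial, but its reasons are confidentiality and separation of roles. They do not touch this selection.

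**Working it through.** **1. The plan's own figure.** With 500 per arm and 80% success in both, the SE of the log risk ratio is sqrt(0.2/(500 × 0.8) + 0.2/(500 × 0.8)) = 0.0316. The interval is exp(±1.96 × 0.0316) = 0.940 to 1.064, which matches the stated 1.00 (0.94, 1.06) in SAP section 3. That figure is not in dispute.

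**2. Who is analysed, among patients randomised too recently to have reached Visit 199.**

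| Status at the stop | SAP 2.11 | SAP 2.5.3 | Result |
|---|---|---|---|
| On drug, in follow-up | excluded | overridden by 2.11 | dropped |
| Died or fully withdrawn | does not apply | failure | kept as failure |
| Off drug, still followed to Visit 199 | excluded if read literally | failure | sections conflict |

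**3. Formula.** Per arm, let n be the patients past week 10 at the stop, m those randomised in the last 10 weeks, p the true success rate and f the share of m already failed and kept.

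- Reported rate = n·p/(n + m·f)
- Reported risk ratio = true risk ratio × (n + m·f_post)/(n + m·f_pre)

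If f is the same in both arms, the risk ratio does not change.

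**4. Inputs.**

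- From the documents: interim looks at 30% and 60% of about 1000 patients, randomised 1:1, so n = 150 or 300; planning success of 80%; primary analysis in the SAF.
- Assumed, because the documents give neither recruitment speed nor within-trial dropout: 100 to 300 patients in total randomised in the last 10 weeks (m = 50 to 150); uniform entry; constant hazard after first dose. Where timing differs, first dose is put at 0.5 weeks (Pre-discharge) and 2.5 weeks (Post-discharge), in line with the start windows in Protocol 3.1.
- Assumed failure shares by week 10: 5% for deaths and withdrawals alone; 10% to 20% when drug-stoppers are included. For orientation only, Protocol 3.6 reports 10.4% permanent discontinuation in the run-in of the earlier enalapril-controlled trial.

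With lag L weeks and share q failed by week 10, f = ((10 − L)/10) × (1 − q/(−ln(1 − q))).

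**5. Only deaths and withdrawals kept (q = 5%).**

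- No lag: f = 1 − 0.05/0.0513 = 0.0252. With n = m = 150, 120/(150 + 3.8) = 78.0%. With n = 300 and m = 50, 240/(300 + 1.3) = 79.7%. The true rate is 80%.
- With the lags, n = m = 150: (150 + 2.8)/(150 + 3.6) = 0.995. The range over all cases is 0.995 to 1.000, for a true 1.00.

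**6. Drug-stoppers also kept.**

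- Equal shares (10% to 20%) and equal timing: a true 80% is reported as 72.5-78.7% at the 30% stop and 76.1-79.3% at the 60% stop. The risk ratio stays 1.00.
- Equal shares, different timing: risk ratio 0.981 to 0.998 instead of 1.00.
- True 75% against 80% (risk ratio 0.938), with 15-20% Pre-discharge and 10% Post-discharge off drug: 0.886 to 0.932. The low end is n = m = 150 with 20% against 10%: 112.5/(150 + 14.8) = 0.683, 120/(150 + 5.7) = 0.771, ratio 0.886.
- The same 20% against 10% at the 60% stop with m = 150: 0.911 (0.831, 0.997), against 0.938 (0.860, 1.022) when selection is by date alone.

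**7. Latest scheduled Visit 199.** Under Protocol 3.1, a prolonged-stay Post-discharge patient may start drug up to 21 days after randomisation. That day becomes Visit 103, and later visits run from it. Visits 104, 105, 106 and 199 follow at two-week steps: 21 + 4 × 14 = 77 days, or 80 with the 3-day window.

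**The case against.** The strongest reply concerns patients who have stopped drug. They remain in follow-up, so a termination does cause their missed Visit 199. Section 2.11 is the specific rule and, read literally, excludes them just as it excludes patients doing well. Only deaths and full withdrawals are then kept, and step 5 shows how little that does. This largely stands. It does not clear the plan, because 2.5.3 makes the same patients failures without exception and nothing says which section prevails.

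A reader might infer that the rule exaggerates the very difference that led to the stop. The documents do not support that. The listed DMC reviews (Protocol 9.6.1, SAP 2.11) cover adverse events, medication changes and washout compliance; week-10 success is not listed. The exclusion applies to the up-titration analyses only, so the adverse event summaries, including those counted from randomisation (SAP 2.8.1), are untouched. SAP 5.4.1 plans no statistical test, so an interval that shifts past 1 decides nothing formally.

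The clause may also be spent. The SAP history labels the latest amendment as preceding the final database lock, the first lock follows completion of week 10 by all patients, and no stop is mentioned. That the first lock had already happened is an inference, but it limits the practical weight.

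**Conclusion.** The selection on outcome is certain from the text for patients who have died or fully withdrawn, and unresolved for patients off drug but still followed. Its direction is downward for the success rate in any arm with early failures. A bias in the risk ratio does not follow automatically: it needs early failures to differ between arms in number or timing. That is plausible, since the Pre-discharge arm starts drug sooner.

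A reader might go further and infer that every early drug-stopper is certainly kept as a failure, and so that the risk ratio is materially distorted. The larger shifts in step 6 depend on that reading, and also on unequal stopping rates or timing that the documents do not give. On the literal reading of 2.11 the effect on the risk ratio is at most about half a percent under the assumed 5%. The point deserves a clear sentence in the SAP; it is not a threat to a trial that runs to completion.

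**What to change.** Replace the sentence in SAP 2.11 with a rule on randomisation date alone. Suggested content: after a DMC termination, the primary and supplementary analyses include only patients randomised at least 80 days before the termination date, with the same cut-off in both arms; everyone randomised later is left out whatever their status; SAP 2.5.3 applies without exception to those included. List the outcomes of the excluded patients separately, with deaths and discontinuations shown. Add the rule to SAP section 4.

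A cut-off of 10 weeks plus 3 days (73 days) would be too short: prolonged-stay patients with Visit 199 due as late as day 77 could be kept without having reached it, in the Post-discharge arm only.

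The cost is one sentence and some data. Known failures among recent patients leave the primary table, as do recent completers. On the ordinary schedule Visit 199 falls at day 70, so about 80 − 70 = 10 days of recruitment are lost; at the assumed 100 to 300 patients per 70 days, that is about 14 to 43 patients. The by-date interval in step 6 uses a plain 10-week cut-off, so with 80 days it would be slightly wider.

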### 3 Sample size calculation

The purpose of this study is to explore two modalities (Pre-discharge, and Post-discharge) of treatment initiation with LCZ696 in HFrEF patients following stabilization after an ADHF episode.

A sample size of about 1000 patients provides reasonable precision across a range of possible outcomes. When the observed rate of 10-weeks up-titration treatment success is 80% in both pre- and post-discharge, it will provide estimated risk-ratio and 95% CI of 1.00 (0.94, 1.06).

Observed rate of up-titration success at week 10 after Randomization		Risk ratio (Pre-discharge / Post-discharge)	2-sided 95% CI	Total sample size without adjustment
Late initiation	Early initiation			
75%	70%	0.93	0.87, 1.01	1000
75%	75%	1.00	0.93, 1.07	1000
75%	80%	1.07	1.00, 1.14	1000
80%	75%	0.94	0.88, 1.00	1000
80%	80%	1.00	0.94, 1.06	1000
80%	85%	1.06	1.00, 1.13	1000

### 4 Change to protocol specified analyses

- The definition of the full analysis set (FAS) was updated to exclude patients who have inadvertently been randomized, regardless the study medication intake.
- The definition of the safety analysis set (SAF) was updated to exclude patients who have inadvertently been randomized, regardless the study medication intake.
- Creatinine kinase parameter is not analyzed as the data have not been collected.

## 5 Appendix

### 5.1 Imputation rules

#### 5.1.1 Study drug

Start date and end date of study drug on the respective CRF panel are mandatory; thus no date imputation will be applied.

#### 5.1.2 AE date imputation

##### 5.1.2.1 Adverse Event End Date Imputation

###### Rules for imputing the AE end date

1. If the AE end date month is missing, the imputed end date should be set to the earliest of the (treatment follow-up period end date, 31DECYYYY, date of death).
2. If the AE end date day is missing, the imputed end date should be set to the earliest of the (treatment follow-up period end date, last day of the month, date of death).
3. If AE year is missing or AE is ongoing, the end date will not be imputed.

##### 5.1.2.2 Adverse Event Start Date Imputation

###### Rules for imputing the AE start date

The following table explains the notation used in the logic matrix. Please note that **missing start dates** will not be imputed.

	Day	Month	Year
Partial Adverse Event Start Date	Not used	MON	YYYY
Treatment Start Date	Not used	TRTM	TRTY

The following matrix explains the logic behind the imputation.

	MON MISSING	MON < TRTM	MON = TRTM	MON > TRTM
YYYY MISSING	( 1 ) No convention	( 1 ) No convention	( 1 ) No convention	( 1 ) No convention
YYYY < TRTY	( 2.a ) Before Treatment Start	( 2.b ) Before Treatment Start	( 2.b ) Before Treatment Start	( 2.b ) Before Treatment Start
YYYY = TRTY	( 4.a ) Uncertain	( 4.b ) Before Treatment Start	( 4.c ) Uncertain	( 4.c ) After Treatment Start
YYYY > TRTY	( 3.a ) After Treatment Start	( 3.b ) After Treatment Start	( 3.b ) After Treatment Start	( 3.b ) After Treatment Start

Before imputing AE start date, find the AE start reference date.

1. If the (imputed) AE end date is complete and the (imputed) AE end date < treatment start date then AE start reference date = min (informed consent date, earliest visit date).
2. Else AE start reference date = treatment start date

Impute AE start date -

1. If the AE start date year value is missing, the date uncertainty is too high to impute a rational date. Therefore, if the AE year value is missing, the imputed AE start date is set to NULL.
2. If the AE start date year value is less than the treatment start date year value, the AE started before treatment. Therefore:
  - a. If AE month is missing, the imputed AE start date is set to the mid-year point (01JulYYYY).
  - b. Else if AE month is not missing, the imputed AE start date is set to the mid-month point (15MONYYYY).
3. If the AE start date year value is greater than the treatment start date year value, the AE started after treatment. Therefore:
  - a. If the AE month is missing, the imputed AE start date is set to the year start point (01JanYYYY).
  - b. Else if the AE month is not missing, the imputed AE start date is set to the later of (month start point (01MONYYYY), AE start reference date + 1 day).
4. If the AE start date year value is equal to the treatment start date year value:
  - a. And the AE month is missing the imputed AE start date is set to the AE reference start date + 1 day.
  - b. Else if the AE month is less than the treatment start month, the imputed AE start date is set to the mid-month point (15MONYYYY).
  - c. Else if the AE month is equal to the treatment start date month or greater than the treatment start date month, the imputed AE start date is set to the later of (month start point (01MONYYYY), AE start reference date + 1 day).

If complete (imputed) AE end date is available and the imputed AE start date is greater than the (imputed) AE end date, then imputed AE start date should be set to the (imputed) AE end date.

### **5.1.3 Concomitant medication date imputation**

#### **5.1.3.1 Concomitant medication end date imputation**

Rules for imputing the CM end date:

1. If CM end day is missing and CM month/year are non-missing then impute CM day as the earliest of treatment follow-up period end date, last day of the month, date of death.

2. If CM end day/month are missing and CM year is non-missing then impute CM day as the earliest of treatment follow-up period end date, 31DECYYYY, date of death.
3. If CM day/month/year is missing then use the treatment follow-up period end date as the imputed CM end date. No imputation is performed when the concomitant medication start date is on or after the end of study visit.
4. If imputed CM end date is less than the CM start date, use the CM start date as the imputed CM end date.

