5.5.8 Prohibited treatment

ACEIs, ARBs and direct renin inhibitors such as aliskiren

In this clinical trial, patients' pre-study ACEIs/ARBs will be replaced with LCZ696.

Due to the potential risk of angioedema when used concomitantly with an ACE inhibitor, LCZ696 must not be started for at least 36 hours after discontinuing ACE inhibitor therapy.

LCZ696 should not be co-administered with an ARB due to the angiotensin II receptor blocking activity of valsartan.

The concomitant use of any ACEIs or ARBs is strictly prohibited while the patient is receiving LCZ696. If the investigator believes that addition of an ACEI or ARB is necessary, then LCZ696 must be discontinued. If treatment with LCZ696 is stopped, ACE inhibitor therapy must not be initiated until 36 hours after the last dose of LCZ696.

Concomitant administration of direct renin inhibitors, such as aliskiren is also prohibited in this study.

Other medications

Bile acid sequestering agents, such as cholestyramine and colestipol are **prohibited** to avoid interference with study drug absorption.

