#### **2.4.2 Prior, concomitant and post therapies**

Prior or concomitant medications will be summarized for the safety set in separate tabulations based on the coding dictionary used. Prior and concomitant medications used during the randomized phase will be summarized by therapeutic class, preferred term and treatment group.

The SAF population will be used for the above analyses.

Prior medications are defined as drugs taken prior to index hospital admission. Concomitant medication is any medication given at least once post-admission and the last day of the study, including those which were started pre-admission and continued post-admission. Prior or concomitant medication will be identified based on recorded or imputed start and end dates of medication taking. Medications administered during the acute treatments of the decompensated heart failure event (from admission to the time of signing ICF) will NOT be included in the CRFs. Concomitant medication at discharge will be summarized separately.

Per protocol, HF-related therapy starting after the End of Study (to ensure adequate chronic treatment after conclusion of study participation) is also reported. This therapy is HF-specific and may start either on the same day of EoS or as late as 10 days later due to availability in the country of the commercial product, and also considering the needed 36-h washout that may be

needed to resume ACEI treatment after ending study medication administration. A separate table will be compiled indicating the treatment started after End of study Visit.

Prior and concomitant heart failure and cardiovascular-related medications will be summarized separately at separate time points. To be consistent with LCZ696B2314, here are the medications that will be summarized:

- ACEi\*
- ARBs\*
- Beta-blocking agents\*
- Diuretic\*
- Loop diuretics
- Thiazide
- Other Potassium sparing diuretics
- Mineralocorticoid receptor antagonists (MRAs)\*
- Digoxin
- Cardiac glycosides\*
- Calcium Channel Blockers (CCB)/Calcium antagonist\*
- Nitrates\*
- Other vasodilators\*
- Oral anticoagulant\*
- Other antiplatelet agents\*
- Aspirin\*
- Antiarrhythmic agent\*
- Statins\*
- Other lipid lowering agents\*
- Simvastatin
- Inotropic agents

Note: those with an asterisk will be included additionally in a figure

The classes of medications will be defined in a separate file with ATC preferred term and WHO drug code.

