The compliance with 36-hour washout from ACEi strata will also be summarized.

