### **5.1.3.5 Other imputations**

There are currently no other imputation rules.

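### SAP 5.1.3.1 moves incomplete ACEI/ARB stop dates to the latest possible day with no link to the first LCZ696 dose, so medication tables (and the washout summary, if it uses imputed dates) can show overlap that never occurred

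*SAP*

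**What the plan says.** SAP 5.1.3.1 has three rules for an incomplete medication end date:

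- Day missing: "If CM end day is missing and CM month/year are non-missing then impute CM day as the earliest of treatment follow-up period end date, last", and the list of candidates then closes with month end and date of death.
- Day and month missing: "impute CM day as the earliest of treatment follow-up period end date, 31DECYYYY, date of death".
- Whole date missing: "If CM day/month/year is missing then use the treatment follow-up period end date as the imputed CM end date".

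None of them refers to the first LCZ696 dose, and none treats ACEI or ARB differently from other drugs. SAP 5.1.3.5 adds: "There are currently no other imputation rules".

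The imputed dates are used. SAP 2.4.2 says: "Prior or concomitant medication will be identified based on recorded or imputed start and end dates of medication taking". The same section plans tables of heart failure drug classes, including ACEi and ARBs, at separate time points, and a separate summary of concomitant medication at discharge. It ends with: "The compliance with 36-hour washout from ACEi strata will also be summarized". Compliance with the ACEI washout and with stopping ARBs is also on the DMC's review list (Protocol 9.6.1, SAP 2.11).

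Protocol 5.5.8 states: "The concomitant use of any ACEIs or ARBs is strictly prohibited while the patient is receiving LCZ696". Protocol 3.1 requires 36 hours between the last ACEI dose and the first LCZ696 dose, and has LCZ696 take the place of the next scheduled ARB dose. SAP 5.1.1 makes study drug dates mandatory, so the LCZ696 start date is always known.

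**The concern.** A latest-possible end date is a sensible default for most drugs. For ACEI and ARB it resolves all the uncertainty in one direction. The true stop should fall a short time before a known date, the first LCZ696 dose, and the rule pushes the stop later without looking at that date. Other imputation rules in the SAP do use an anchor: partial adverse event start dates are set relative to treatment start (5.1.2.2), and partial medication start dates relative to index admission (5.1.3.2).

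At stake is how the ACEI/ARB tables read. Combined use with LCZ696 is prohibited, and the ACEI washout is there because of angioedema risk (Protocol 3.6). A table that mixes real overlaps with products of a date rule says less about how well the switch was carried out.

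**Working it through.** The documents give no count of incomplete dates and no washout failure rate, so there is no planned figure to reproduce. What can be checked is how often the rule would carry a compliant stop past the first LCZ696 dose.

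**Inputs.** From the SAP: the three rules in 5.1.3.1. Assumed: true stop dates spread evenly over a 365-day year, and a gap of g days between the true stop and the first LCZ696 dose. Short gaps match the switch described in Protocol 3.1. Post-discharge patients may also stay on ACEI/ARB until they switch. Longer gaps are shown because the protocol sets no maximum.

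**One record.** Last ACEI dose on 3 March with the day not recorded; first LCZ696 dose on 5 March. The imputed stop is 31 March, so the apparent overlap is 5 to 31 March, which is 27 days.

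**Day missing.** A stop on day d of a month with L days moves to day L. The first dose is on day d + g. Overlap appears when d + g ≤ L, which holds for L − g of the L days. Over 12 months that is 365 − 12g days (valid for g up to 28). The last column counts imputed ends less than 2 calendar days before the first dose, or later: 365 − 12(g − 1) days.

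| Gap g (days) | Imputed end on or after first dose | Imputed end less than 2 days before first dose, or later |
|---|---|---|
| 1 | 353/365 = 96.7% | not informative (true gap already under 2 days) |
| 2 | 341/365 = 93.4% | 353/365 = 96.7% |
| 3 | 329/365 = 90.1% | 341/365 = 93.4% |
| 7 | 281/365 = 77.0% | 293/365 = 80.3% |
| 14 | 197/365 = 54.0% | 209/365 = 57.3% |
| 21 | 113/365 = 31.0% | 125/365 = 34.2% |

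The cut at follow-up end or death does not change the overlap column. In a treated patient neither comes before the first dose, so the cut only shortens the overlap.

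**Day and month missing.** The share with overlap is (365 − g)/365: 364/365 = 99.7% at 1 day and 344/365 = 94.2% at 21 days.

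**Whole date missing.** The imputed stop is the end of follow-up, so the overlap spans the patient's whole LCZ696 exposure.

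**Scale.** These are percentages of incomplete records, not of patients. The protocol caps ACEI- or ARB-treated patients at 930. If 1%, 3% or 5% of them had a day-missing stop (an assumption):

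- 2-day gap: 930 × share × 0.934 = about 9, 26 or 43 false overlaps.
- 14-day gap: 930 × share × 0.540 = about 5, 15 or 25.

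**Where it would show.** Protocol 3.1 has Pre-discharge patients take LCZ696 at least 12 hours before discharge, with ACEI/ARB already stopped. A day-missing stop in the month of discharge is imputed to month end, so the patient appears on ACEI/ARB at discharge. Post-discharge patients may properly be on ACEI/ARB then, so the artefact also blurs the comparison between arms in that table.

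**Washout.** Calendar dates cannot settle a 36-hour criterion. Dates two days apart can mean anything from just over 24 to just under 72 hours. The last column above is therefore only a rough stand-in.

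**The case against.** The strongest reply is that the SAP never says imputed dates enter the washout summary. SAP 2.4.2 uses them to label medication as prior or concomitant, and it gives no data source for washout compliance. Details of the DMC item are left to the DMC Charter and an interim analysis plan. This stands: false washout failures are conditional on a choice the SAP leaves open.

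Nor is a table of ACEI/ARB taken together with LCZ696 described. The SAP ties the word concomitant to index admission, so an ACEI continued into hospital carries that label whatever its end date. This also stands. The exposure is through the time-point and discharge tables.

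Incomplete ACEI/ARB stops may be few. The stop is a deliberate step close to the first dose, medication after consent goes into the CRF, and the week-10 lock requires queries to be resolved. That makes a small number plausible but does not guarantee it.

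Finally, a late end date can be called conservative because it hides no exposure. That is fair for a general medication table. It is weaker for a compliance summary, where a possible breach should not be shown as an observed one.

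**Conclusion.** The point holds in a limited form. The SAP has a stated rule, with no exception, that would place most day-missing ACEI/ARB stops after the first LCZ696 dose: about 93% at a 2-day gap and 54% at 14 days. These figures assume evenly spread stop dates and apply only to incomplete records, whose number is unknown. Stops in one month with LCZ696 started in the next escape the day-missing rule.

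A reader might go further, in three ways that the documents do not support:

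- *Patients who stopped in time are counted as washout failures.* That depends on an unstated data source, and it can concern ACEI only, since ARB has no washout.
- *Real breaches cannot be told from artefacts.* Breaches with complete dates are untouched by the rule, and listings of individual patient data are planned.
- *Trial conclusions are at risk.* The primary endpoint is the dose at week 10, and the secondary endpoints concern dose maintenance and discontinuation. No exclusion in SAP Tables 5-1 and 5-2 rests on prohibited medication or washout. Only descriptive tables and the DMC item could be affected.

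It is still worth correcting, because the repair is small and the drug class is the one whose stop matters most.

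**What to change.** Add to SAP 5.1.3.1, with a cross-reference in 2.4.2:

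*The ACEI washout summary, and any table of ACEI or ARB use at or after the first LCZ696 dose, uses recorded stop dates only (and times where collected). If the known parts of the date allow a stop on either side of the relevant limit, or the date is wholly missing, the record is shown in a separate row, stop date incomplete, not evaluable, and listed. Such records are neither counted as violations nor dropped.*

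Where the known parts settle the question, for example a stop month well before the LCZ696 start, the record is classified as usual. The SAP should also name the data source for the washout summary, and the interim analysis plan should follow the same rule. Keep the general rule for all other drugs.

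The cost is one SAP paragraph, one extra table row and a not-evaluable category that is likely to be small. No clinical rule changes.
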